5.2 Household survey data

Quantitative data from surveys will be compared among areas (for BBnet barrier suspension) and time points (for BBnet barrier suspension, net durability assessments, and ordinal questionnaire data) using ANOVA, t-tests or non-parametric equivalents as appropriate. For qualitative data, coding will use Atlas.ti v9.

6. Data recording, management and confidentiality

The clinic nursing staff and assistants are familiar with the procedures involved, which are routine, and training will be provided to the appointed member of clinic staff who will be a part of the wider study team and responsible for ensuring the protocol is followed and data recording occurs correctly. The study team will be in contact via telephone with the study-associated member of the clinic staff to emphasise key points and answer queries. The DRC project PI will be responsible for coding the data so that data analysis will be performed blind to the identity of clusters by another member of the study team (at LSTM). Data will be entered into an Access database as soon as possible after data collection. All data collected will be anonymous, and GPS locations of individual houses will not be used in any report or presentation. Any photographs taken will only be taken of bednets and will not show residents.

7. Ethical considerations

7.1 Vulnerable groups

The epidemiological component of the study involves solely pregnant women presenting at their first antenatal clinic, which is expected to be early in their second trimester. Though pregnant women can be classed as a vulnerable group the study is requesting to administer tests which are given routinely to people presenting with a fever and ACT treatment is the WHO and DRC standard for women outside of their first trimester. We will not include pregnant women presenting with severe malaria symptoms, for whom urgent treatment and admission to hospital, as per standard guidelines, would be the priority rather than ANC procedures. Pregnant adolescents (<15 years) are expected to represent a small proportion of the cohort at ANCs and will not be enrolled. However, based on data from DRC as a whole (MPSMRM 2013-14) we estimate that approximately 18% of the ANC visitors are likely to be in the 15-18 (older adolescent) grouping, therefore exclusion would represent a significant source of bias. This cohort does constitute a vulnerable group because of their age but in many cases pregnant women in this cohort will be married and living independently of their parents/ guardians who may not accompany them to the ANC. To allow representative sampling we therefore propose to include pregnant older adolescents with their consent and their parental/ guardian consent if present, but with their consent alone if they are not accompanied by a parent or guardian. The questionnaire for the ANC visitors is short and is not designed to request sensitive or personally-identifiable information.

7.2 Household surveys

7.2.1 During visits and surveys, householders may have concerns about their privacy or security of their home.

Mosquito sampling and net hanging evaluation should cause nothing more than mild inconvenience, but if there are very old/ infirm householders we would ensure that they are able and happy to exit a room for a short time during the mosquito collection period. If this is not the case and sampling could not occur without disturbing the resident, we would advise against consent. Interviews will be carried out by personnel experienced in qualitative data collection methods to ensure culturally sensitive approaches are followed to reduce undue stress to participants.

7.2.2 Skin/respiratory irritation from use of the nets distributed or provided as replacements

The nets are distributed by the national malaria control programme and have a very good safety record. Since P3-BBnets are identical in all relevant aspects to PermaNet 3, there is no expectation for any differential safety concerns.

7.2.3 COVID19 transmission

Survey teams will follow current national guidelines on use of masks and gloves as appropriate to avoid any enhanced risk to householders.

8. Safeguarding

The safeguarding issue we identify is Empowerment as it relates to the informed consent procedure. The study population may comprise of individuals with low educational and socio-economic status. For this reason we keep the participant information leaflet as simple as possible, and the study will be explained to participants or householders carefully, being particularly clear about the right to refuse participation without any prejudice to standard care. No incentives or coercion will be used by clinic staff or mosquito collection staff to obtain consent. Nursing staff responsible for recruitment will receive training from the study team to recognise and avoid any possibility of coercion.

9. Dissemination

The findings of the research will be made available to the net distributor AMF, and National Malaria Control Programme for onward dissemination as soon as available, and later published in open access journals. Presentations will be made to key stakeholders in DRC, and findings will be made available to the WHO.

10. Project timeline

Month_Year	Sep_23	Oct_23	Nov_23	Dec_23	Jan_24	Feb_24	Mar_24	Apr_24	May_24	Jun_24
Months after net distribution	4	5	6	7	8	9	10	11	12	
Project month	1	2	3	4	5	6	7	8	9	10
Preparation and training										
Liaison with SANRU, PNLP, health service										
Ethics										
Staff recruitment										
Training of health centre staff										
Collection of GPS for health centres										
Surveys										
ANC monitoring										
Entomology (community collections)										
Householder questionnaires										
Entomological sample processing										
Physical assessment of nets (KSPH)										
Molecular analysis of ento samples (LSTM)										
HPLC analysis of nets (LSTM)										
Analysis and reporting										
Data analysis										
Final reporting										

11. References

Accrombessi M, et al. 2023. Efficacy of pyriproxyfen-pyrethroid long-lasting insecticidal nets (LLINs) and chlorfenapyr-pyrethroid LLINs compared with pyrethroid-only LLINs for malaria control in Benin: a cluster-randomised, superiority trial. Lancet https://doi.org/10.1016/S0140-6736(22)02319-4

12. APPENDICES (A-F)

QUESTIONNAIRE v2.1

E. TO BE ADMINISTERED TO PREGNANT WOMEN DURING THEIR FIRST ANTENATAL CLINIC VISIT

Version Date 18/09/2023

Questionnaire number :

Corresponding ANC sheet number :

Line number in the ANC register :

Visit date : /...../..../...../...../

Question	Questions	Items	Answer			
number			code			
	Section 1 : Particip	bant details				
Note : que asked	Note : questions marked * are to be completed by the staff member, rather than being asked					
Q1.1	Date of birth	///				
Q1.2	Age	years				
Q1.3	Occupation					
Q1.4	In which village do you live?					
Q1.5*	Is your village inside this health area or in another health area?	 This area Another area 				
Q1.6*	If in another – which health area?					
Q1.7*	Approximate distance from the					

	village to this clinic?	
Q1.8	How many months pregnant are you?	
Q1.9	How many children have you had previously?	
Sec	ction 2 : Prevention and risk behaviour	relating to malaria in the household
Q2.1	Do you use insecticide-treated bednets in the household?	1. Yes 2. No
Q2.2	If no, ask why?	 a. Bednets not delivered to house during distribution campaign b. Bednets available are damaged c. Bednets given to others d. Other reason (please specify)
Q2.3	How many LLINs are present in your household?	
Q2.4	Among these LLINs, do you use one regularly?	1. Yes 2. No
Q2.5	Did you spend last night under an LLIN ?	1. Yes 2. No
Q2.6	If no – ask why?	
Q2.7	Other than bednets do you use any other method of mosquito control in your home ?	1. Yes 2. No
Q2.8	If yes, why ?	
Q2.9	Which additional methods do you use?	
Q2.10	What time do you usually go to bed?	

Q2.11	How many people live in your		
	house ?		
	Section 3: Questions a	bout P3-BBnets	
Q3.1	Did you receive bednets with a	1. Yes	
	barrier to hang above the net roof as	2. No	
	part of the programme		
		If no, go to section 4	
Q3.2	What is the most common way that		
	the barrier above your way is suspended (refer to picture)	1. 25%	
		2. 50%	
		3. 75%	
		4. 100%	
	25%	50%	
	75%	100%	
Section 4:	MALARIA TEST RESULT		
Q4.1*	What is the result of your malaria test?	 Positive Negative 	

QUESTIONNAIRE v2.1

F. TO BE COMPLETED WITH HEAD OF HOUSEHOLD OR REPRESENTATIVE

Version Date 18/09/2023

Questionnaire number :

Visit date : /...../...../...../...../

Health zone :

Health Area :

Household Identification number:....

Household GPS coordinates:/...../

Team members present :

SECTI	SECTION 1: Household questionnaire			
Q1.1	Respondent's relationship to head of household	1. Head of		
		household		
		2. Partner of		
		head of		
		household		
		3. Child of head		
		of household		
		4. Other		
Q1.1b	If other, specify			
Q1.2	What is the total number of people currently in the household			
	including yourself?	///		
Q1.3	What is the total number of sleeping areas (bedrooms or	//		

	spaces used for sleeping)	
Q1.4	How many LLINs did you receive during the distribution	
	programme?	//
Q1.5	How many of these LLINs are available in the household today?	//
Q1.6	Have you received or purchased LLINs from other sources?	0. No
		1. Yes
Q1.6b	If yes, how many did you receive?	//
Q1.7	Do you have BBnets in your house ?	0. No
	(refer to picture below for identification of a BBnet)	1. Yes
Q1.8	How many BBnets do you have ?	
		//
Q1.9	How many BBnets are used regularly (i.e. most nights) ?	, ,
		//
Q1.10	Do you suspend the barrier of your BBnets	/ /
	1. always 2. sometimes 3. occasionally 4. never	//
Q1.11	If answer to Q10 is s 2-4 : Why is the barrier not suspended ?	
	1. too difficult	/ /
	2. takes too long	/
	3. don't have hanging material (string)	
	4. don't have hooks or nails	//
	5. hooks or nails do not remain in walls	//
	6. broken loops	//
	7. not enough space	//
	8. other	/  
Q1.11	If other, specify	
b		
Q1.12	Do you know what the purpose of the barrier is ?	
	If yes ask ; if answer different from actual purpose mark 'no'	0. No
	and explain the purpose (to kill more malaria mosquitoes as	1. Yes
	they come to bite sleepers under the net)	
Q1.13	Which picture shows how the barrier should be suspended?	
		0. don't know
		1. 25%.
		2. 5U% 2 7E%
		3. 75% 4 100%
		4. 100%
	100%	
	75%	
Q1.14	If you were offered a choice between a BBnet and a PermaNet	0. BBnet

	3, which is identical apart from the absence of a barrier, which		1. P3
	would you choose		
Q1.15	Why is this?		

Section 2 : Household observations (to be completed with householder assistance)				
2.1. What are the main materials used for the construction of the house? Mark with an X				
a. Walls	b. Floor			
Mud	Earth / sand			
Brick	Dung			
cement plaster	Ceramic tiles			
Cement / Paint	Cement			
Other (specify)	Other (specify)			
c. Roof	d. Eaves			
Thatch/palm leaves	Opened			
Metal	Closed			
Other specify :	Partially open			

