2.5. Cluster allocation and bednet distribution

Health areas from within the designated study health zones which have a functional ANC receiving on average ≥25 ANC1 visitors/month (based on DHIS2 data from September 2021-August 2022), form the list from which clusters were randomly-chosen. We will include all the health areas to which P3-BBnets are distributed as clusters for ANC1 monitoring and twice this number of PermaNet 3 clusters, chosen at random from within the same health zones.

Nine Lubumbashi health zones are identified (Fig. 6), which are wholly within Lubumbashi (this excludes Kipushi and Kafubu), and do not have military encampments (this excludes Kowe and Vangu). Within these nine health zones, health areas will by default receive PermaNet 3 unless randomly chosen to receive P3-BBnets. Table 1 shows the nine health zones including estimated projections of net need. In total, 133 health areas were identified (within the nine health zones)

which receive on average ≥25 ANC1 visitors per month and these were included in the list for allocation to be clusters in the study. Using a random number generator, 30 health areas were chosen, of which the first 21 were proposed for coverage by BBnets, with the additional health areas (random numbers 22-30 in order) serving as additions if sufficient P3-BBnets remain after distribution to the first 21, or as backups in case ANCs in any areas are no longer fully-functional or health centres do not wish to participate. The randomised choice was made by a non-study team member and was communicated to the SANRU distribution team.

Distribution of nets occurred under the standard procedures of the PNLP and SANRU distribution programme, which delivers bednets to health areas for distribution by community health workers. Based on the randomised allocation, each health area received bales of the appropriate bednet for onward distribution to households. Bednets are not routinely distributed with hanging materials, but for the P3-BBnets, string and hooks were provided (by the study team) to promote suspension of the barrier. Community health workers were trained to advise householders on the function of the barrier, its potential advantage and how to suspend it. If the householder decides not to suspend the barrier, the P3-BBnet will still provide protection in the same way as a PermaNet 3, given the identical physical and chemical composition of the net material.

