4.1 ANC1 malaria prevalence

Women who visit their first ANC and consent to take part in the study will asked to allow their malaria test result to be recorded and to complete a questionnaire (**Appendix E**) which requests basic demographic information, information on stage of pregnancy and number of previous pregnancies, the type(s) and numbers of bednets and their use, and - *if their household received a BBnet* - the hanging status of the barrier under which they sleep by reference to pictures on the questionnaire form. Additional information will be the health area within which their home is located to identify if this is different from that in which the ANC1 is visited. Test results and questionnaires will be anonymous and no personally-identifiable information will be requested. Data will be recorded onto forms and stored securely at the health facility as well as onto mobile phones to allow prompt electronic transfer to the study team. Monitoring of ANCs will take one during a 3-month window at 7-9 months after the distribution.

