2.2. BBnets (only to be completed if house has BBnets)

2.2a. How many BBnets are hanging	//
2.2b. How many have a barrier suspended according to each category (refer to picture)	1. 25%. // 2. 50% // 3. 75% // 4. 100% //
100%	

2.2c. How many of the nets had a barrier weighed down by clothing?	//
2.2d. How many of the nets did not have hooks or nails present for handing the barrier ?	//

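### Appendix E Q3.2 has no code for a BBnet barrier that is not suspended or a BBnet that is not used, so the adherence record of the ANC women cannot show either

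*Protocol*

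**What the plan says.** Section 4.1 of the Protocol states that, where the household received a BBnet, the ANC questionnaire captures "the hanging status of the barrier under which they sleep by reference to pictures on the questionnaire form".

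Appendix E does this with two items:

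- Q3.1 opens "Did you receive bednets with a" and asks about receipt of a barrier net. Its skip rule is "If no, go to section 4", so every woman whose household received one goes on to Q3.2.
- Q3.2 is printed as "What is the most common way that" followed by "the barrier above your way is suspended (refer to picture". The answer codes are 25, 50, 75 and 100%, keyed to pictures. There is no other code and no instruction for a barrier that is not hung.

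The earlier items on net use (Q2.1, Q2.4, Q2.5) concern any insecticide-treated net and do not identify the type.

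Section 2.5 foresees non-suspension: "If the householder decides not to suspend the barrier, the P3-BBnet will still provide protection in the same way as a PermaNet 3". The household form in Appendix F allows for it. Q1.10 offers "1. always 2. sometimes 3. occasionally 4. never", Q1.11 asks for reasons, 2.2a counts the BBnets hanging, and 2.2b asks "How many have a barrier suspended according to each category (refer to picture".

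Section 5.1 plans intention-to-treat and per-protocol analyses. The reason given for the second is that women may attend a clinic outside their health area of residence. ANC questionnaire items are optional covariables.

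**The concern.** The arms differ only in the barrier. By section 2.5's own account, a woman whose barrier is not suspended has in effect the comparator net, so zero is the most informative value on the scale, and it is the value Q3.2 omits.

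The women who answer Q3.2 are those in whom the primary outcome is measured: 1,575 planned in the P3-BBnet arm (section 2.4, Figure 5). Q3.2 is the only item on their form about how the barrier hangs. If it cannot record zero, the trial cannot say from its own primary-outcome participants how many had the barrier in use. Any analysis that takes Q3.2 as an exposure would mix non-suspenders into the 25% group or lose them as missing.

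**Working it through.** **The plan's own figure.** The plan gives no figure for barrier suspension. The nearest figure is the cluster count in section 2.4, which reproduces:

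- Inputs: prevalences 0.24 and 0.18, two-sided alpha 0.05, power 0.80, cluster ratio 0.5, cluster size 75, intraclass correlation 0.025.
- The individually randomised size of the PermaNet 3 arm is 1,098.
- Design effect = 1 + (75 − 1) × 0.025 = 2.85.
- 1,098 × 2.85 / 75 = 41.7, so 42 PermaNet 3 and 21 P3-BBnet clusters. Power at 42/21 is 0.803.

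Nothing in Q3.2 changes this.

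**Step 1: follow a non-suspender through the form.** Her household received a BBnet, so Q3.1 is yes and she reaches Q3.2. She can be coded 25% or left blank. A blank cannot be told from an unanswered item. A woman who sleeps under another net despite having received a BBnet meets the same choice, because Q2.4 and Q2.5 do not separate net types.

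**Step 2: any suspension.** Let u be the share of recipients whose barrier is not suspended. The documents do not give it, so it is assumed. The true proportion suspending is 1 − u: 90, 70 and 50% for u = 10, 30 and 50%. Every available code is at least 25%, so the proportion with any suspension among coded answers is 100% for every u.

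**Step 3: mean suspension.** Let m be the mean among those who do suspend (assumed).

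- True mean = (1 − u) × m.
- Non-suspenders coded 25%: recorded mean = (1 − u) × m + 25u. The overstatement is 25u, whatever m is.
- Non-suspenders blank and dropped: recorded mean = m. The overstatement is u × m. Since m is at least 25, this is at least 25u, and larger unless every suspender is at 25%.

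With m = 75%:

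| u | True mean | Coded 25% | Blank dropped | Overstatement (points) |
|---|---|---|---|---|
| 10% | 67.5 | 70.0 | 75 | 2.5 or 7.5 |
| 30% | 52.5 | 60.0 | 75 | 7.5 or 22.5 |
| 50% | 37.5 | 50.0 | 75 | 12.5 or 37.5 |

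With m = 50% the dropped-blank overstatement is 5, 15 and 25 points. With m = 100% it is 10, 30 and 50.

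**Step 4: why the record is worth having.** Suppose, as an individual-level illustration that ignores community effects, that 0.18 applies with every barrier suspended and an unsuspended barrier adds nothing. Then P3-BBnet prevalence = 0.24 − 0.06 × (1 − u). For u = 10, 20 and 30% this is 0.186, 0.192 and 0.198, and power at 42/21 clusters is 71, 60 and 49%. That loss would come from non-suspension, not from the form. The form only fails to show it among the ANC women.

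**Step 5: what the household form can show.** Item 2.2b is a count per category, not a forced choice. Hanging BBnets with no suspended barrier are therefore 2.2a minus the sum of the 2.2b counts, and Q1.10 has a code for never. Section 3.2 plans about 200 houses, equally split, so about 100 with P3-BBnets. At an assumed 30% non-suspension, the 95% margin is 1.96 × √(0.3 × 0.7 / 100) ≈ 9 points before allowing for clustering.

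**The case against.** The strongest reply is that this is a gap in a descriptive item. The primary comparison does not use Q3.2. The stated motive for the per-protocol analysis is clinic attendance across health areas, and no dose-response or barrier-adherence analysis of ANC women is specified. All of that stands, and it limits the point.

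A reader might infer three stronger things that the documents do not support:

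- **That Appendix F has the same gap.** It does not. Non-suspension follows from 2.2a and 2.2b by subtraction, and Q1.10 and Q1.11 ask about it directly.
- **That a null result could not be separated into a barrier that does not work and one that was not hung.** About 100 P3-BBnet houses are surveyed, and section 4.4 has hanging positions observed against what is reported. That is arm-level evidence on hanging. It is not linked to individual ANC women, so it cannot classify them.
- **That overstated adherence is demonstrated.** It is conditional on some recipients not suspending and on how staff handle them. The form does not tell staff to enter 25%. If blanks were kept and reported as blanks, the loss would be of information rather than an inflated mean.

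Two further replies have partial force. The pictures are not in the text available, so the 25% picture may show a largely collapsed barrier, but its label would still be 25%. Q2.1, Q2.4 and Q2.5 do record whether nets are used. What they leave open is the woman who uses a net other than the BBnet she received.

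**Conclusion.** The point stands as a defect in one questionnaire item. Q3.2 cannot record a state that section 2.5 foresees and that section 4.1 needs if hanging status is to be captured.

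The 100% figure for any suspension among coded answers follows from the codes alone. The size of the error in the mean rests on an assumed non-suspension share: 25u points if non-suspenders are coded 25% (2.5, 7.5 and 12.5 points at 10, 30 and 50%), and more if blanks are dropped and suspenders average above 25%.

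A reader might go on to infer that the effect estimate is compromised. It is not: the intention-to-treat comparison of prevalence does not use this item. The harm is confined to the adherence description of the ANC women and to any optional covariate or per-protocol analysis that uses Q3.2.

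**What to change.** In Appendix E Q3.2, add 0 = barrier not suspended and 9 = did not sleep under a BBnet / do not know, and reword the item to refer to the net she sleeps under. Item 2.2b of Appendix F needs no change.

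For forms already completed:

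- do not report Q3.2 as the proportion suspending;
- treat blank and 25% as not separable, and say so;
- record the form version in the data set;
- take the proportion not suspended from the household survey.

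The cost is a small revision of the paper and phone forms, with no extra visit, test or sample size. Timing is the main drawback. The form is dated 18/09/2023 and the Protocol 29/02/24, and section 4.1 places monitoring at 7–9 months after distribution. Read from the left, the section 10 timeline puts that at December 2023 to February 2024. If collection is still running, a change leaves two coding versions, which is why the version must be recorded. If it has ended, only the reporting rules apply, and they should be fixed before the arm codes are broken.

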3.2 Household surveys

Following initial contact with community leaders facilitated by health centre staff, boundaries of the health areas will be mapped to delimit the area to be surveyed (and the GPS coordinates of each centre holding an ANC clinic will be recorded). Households within the health area will be visited by study personnel, accompanied by a local resident, typically a member of the community health worker's team. From a starting point, a first house will be chosen and subsequent houses sampled based on separation by approximately 50m. If householders are present, the purpose of the study and nature of the request for participation will be explained to them, and if they are willing to be enrolled the head of the household will be asked to sign a consent form, which will give permission (subject to verbal consent at the time of collection) to visit the house to conduct questionnaires of net use and perceptions. Prospective participants will be given up to 24 hours to decide whether to take part. If they do not wish to take part, or the head of the household), a neighbouring house will be approached. The questionnaire will be taken, and net hanging observed, including the position of barriers in houses with P3-BBnets. A photograph of bednets hanging *in situ*, excluding any people, may be taken subject to specific consent from the householder. An equal

number of P3-BBnet and PermaNet 3 houses will be surveyed. The information leaflet and consent form is provided in **Appendix B**. A total of approximately 200 houses will be sampled.

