4.4 Assessment of bednet hanging and user perceptions by questionnaires

The head of the household or their representative will be asked to take part in completion of a questionnaire (**Appendix F**), to assess their perceptions of the nets provided, any difficulties encountered, and suggestions for improvements either to the nets or the way they are distributed. The sample size is based on that employed in an earlier pilot study of user perceptions conducted by the team in Kinshasa province. During the survey rounds, in all houses which have P3-BBnets the position of the barriers will be recorded by reference to a pictorial scale (**Appendix F**). Where bednets are hanging, observations will be made with the householder - if they consent - to check consistency with the reported hanging position.

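### The household form (Appendix F) tells respondents who get the barrier's purpose wrong that it kills more mosquitoes, just before asking which net they would choose and why

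*Protocol*

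**What the plan says.** Section 4.4 gives the purpose of the household questionnaire: "to assess their perceptions of the nets provided, any difficulties encountered, and suggestions for improvements". Section 3.2 plans about 200 houses, split equally between the arms, with the questionnaire taken first and net hanging observed afterwards.

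The relevant items of Appendix F run in this order:

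- **Q1.7 to Q1.9:** whether the house has BBnets, how many, and how many are in regular use. No skip is printed for a house that has none.
- **Q1.10 and Q1.11:** "Do you suspend the barrier of your BBnets", answered from always to never, then the reasons for not suspending it.
- **Q1.12:** whether the respondent knows what the barrier is for. The instruction reads "If yes ask ; if answer different from actual purpose mark 'no"; the interviewer is then to correct the respondent "and explain the purpose (to kill more malaria mosquitoes as" they come to bite.
- **Q1.13:** "Which picture shows how the barrier should be suspended", with a 'don't know' code.
- **Q1.14:** "If you were offered a choice between a BBnet and a PermaNet" 3. The stem adds that the two nets differ only in the barrier. The codes are BBnet and P3.
- **Q1.15:** the reason for the choice, as free text.
- **Section 2:** "Section 2 : Household observations (to be completed with householder assistance"; item 2.2 counts hanging BBnets and the position of their barriers.

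**The concern.** A preference question should be asked before the interviewer says anything in favour of one of the options. Here a respondent who has the purpose wrong hears from the interviewer that the barrier kills more mosquitoes. That respondent is then told that the nets are otherwise the same, and must pick one. Each step points to the BBnet, and a respondent with no view has no code to use. Q1.15 is exposed in the same way, because a reason such as 'it kills more mosquitoes' may only repeat what was said a minute earlier.

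What is at stake is the user-perception result. Section 9 sends the findings to the net distributor, the national programme and the WHO, and a stated preference for the BBnet over the PermaNet 3 is easy to cite. If part of it was produced by the form, it overstates acceptability, and the data as collected cannot show by how much.

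**Working it through.** The point rests on item order, so the check is mainly a reading of the form. The protocol gives no figure for this item to reproduce.

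**1. Who is told.** The instruction at Q1.12 directs the explanation to respondents whose answer differs from the actual purpose. Those who know the purpose are not told. What happens after a plain 'no' is unclear from the wording.

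**2. What is recorded before the explanation.** Q1.8 to Q1.11 cover BBnets owned, regular use, suspension and the reasons for not suspending. None of these can be influenced by Q1.12.

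**3. What is recorded after it.** Q1.13, Q1.14, Q1.15 and Section 2.
- Q1.13 is a knowledge test, and the form does not tell the interviewer to reveal the answer. Its pictures also form the scale for recording hanging at item 2.2b.
- Q1.14 and Q1.15 are opinions, which a favourable message can move.
- Item 2.2 records the physical state of nets already hanging.

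So Q1.14 and Q1.15 are the exposed items, and no earlier item holds an uninfluenced preference.

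**4. Which houses.** In Section 2.5, community health workers were trained to explain the barrier's function and possible advantage to householders receiving P3-BBnets. PermaNet 3 houses were not part of that briefing and are likelier to get Q1.12 wrong if asked. Whether they are asked is not settled. Appendix E prints a skip at its BBnet item (Q3.1), and item 2.2 of Appendix F is restricted to houses with BBnets, but Q1.7 prints nothing. Read as printed, PermaNet 3 houses go on to Q1.12 to Q1.15. Q1.10 makes no sense for them, so interviewers may skip the block in practice.

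**5. Scale, on assumptions only.** Let u be the share of respondents who are told, and s the share who switch from P3 to BBnet among those told who would otherwise choose P3. Assume that half of those told would otherwise choose P3. Then

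shift in stated BBnet preference = u × 0.5 × s.

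- Low: u = 0.20, s = 0.10 gives 0.20 × 0.5 × 0.10 = 0.01, or 1 point.
- Middle: u = 0.50, s = 0.30 gives 0.50 × 0.5 × 0.30 = 0.075, or 7.5 points.
- High: u = 0.80, s = 0.50 gives 0.80 × 0.5 × 0.50 = 0.20, or 20 points.

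For comparison, the 95% half-width of a proportion p from n houses is 1.96 × √(p(1 − p)/n). With about 100 houses (200 / 2 arms) it is 9.8 points at p = 0.50, 9.0 at 0.70 and 7.8 at 0.80, ignoring clustering. The protocol states no precision for this survey. None of u, s, the one half or p comes from the documents. The range shows only that the shift could be negligible or could exceed sampling error.

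**The case against.** The strongest reply is that the message belongs to the intervention. BBnet households were meant to hear the same thing at distribution (Section 2.5), so Q1.12 repeats what the programme already said, and an informed preference is a reasonable thing to want. This stands in part: the added influence is probably smaller in the BBnet arm. It does not rescue the item, because the form does not measure an informed preference either. It informs only those who answered wrongly, so Q1.14 mixes respondents who already knew, respondents just told, and possibly some never told.

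A second reply is that this is one descriptive item. Section 4.4 does not call it a main result, and Section 5.2 names barrier suspension, durability and ordinal questionnaire data but not this binary choice. That is right, and it limits the weight of the point.

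A reader might go further and infer three things that the documents do not support:

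- **That hanging data are tilted too.** Self-reported suspension comes before the explanation. Observed suspension could change only if someone rehung a barrier during the visit. The householder's assistance in Section 2 makes that possible, but nothing suggests it happens.
- **That respondents are told the trial's hypothesis.** The protocol presents greater mosquito killing as already shown in laboratory and hut work (Sections 1.2 and 2.2). The trial tests malaria prevalence at ANC1 and leaves out between-arm entomological endpoints (Section 2.1).
- **That the local guide biases answers.** Study staff are "accompanied by a local resident, typically a member of the community health" worker's team (Section 3.2). The text does not say that this person sits in on the interview.

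**Conclusion.** The point holds for Q1.14 and Q1.15 only. As printed, the form leads respondents who did not know the barrier's purpose toward the BBnet, with no uninfluenced measure to fall back on and no neutral code. The direction is clear from the order and wording. The size is unknown: it depends on how many respondents fail Q1.12 and how readily they switch, and on whether PermaNet 3 houses answer these items. The primary outcome and the hanging item completed at ANC1 come from Appendix E, which contains no such explanation. This is a free improvement to a descriptive measure and does not threaten the trial's main comparison.

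**What to change.** In Appendix F:

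1. Place Q1.14 and Q1.15 directly after Q1.11, before Q1.12.
2. Add a 'no preference' code to Q1.14.
3. Let Q1.12 record knowledge only, and give the explanation at the end of the visit, after Section 2. The householder still receives it.

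Keep the questionnaire before the observation. Section 4.4 uses the observation to check the reported hanging position, and inspecting the nets first would make that report less independent.

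The cost is a reordered form with one added code, and no extra visits, staff or interview time to speak of.

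If the survey is already done, report stated preference by Q1.12 code and by arm (so far as PermaNet 3 houses were asked), and state the question order beside the result. This discloses the problem but does not remove it: not knowing the purpose and having been told it coincide in the same respondents, so their uninfluenced preference cannot be recovered.
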